## **9.2 Sample Size and Randomization**

Assuming a standard deviation of BPI interference of 2.4 (as observed in a previous study (SCOPE)), a total sample size of 610 subjects (305 per group) would provide 80% power to detect a mean difference in BPI interference of 0.55 between groups at 4 months using a two-sided t-test at significance level  $\alpha=0.05$ , and 90% power to detect a difference of 0.63. To account for an expected attrition rate of 20%, we will enroll a total of 764 participants (382 per group). Half of the participants will be female.

Although the randomization will be done at the patient level, there may be some clustering due to the therapist delivering the intervention. We conducted a simulation study to investigate the effect of this clustering on power. We assumed that in the COPEs arm (treatment delivered remotely by IVR) 9 therapists will be delivering the intervention (each to an equal number of subjects), and in the synchronous CBT arm 38 therapists will be delivering the intervention. Based on a prior pain trial of group cognitive behavioral treatments, we used an estimate of therapist-level intracluster correlation coefficient (ICC) of 0.01. Simulations (N=100000) showed that we will

have at least 84% power to detect a difference in BPI of 0.65 with an ICC of 0.01 or less using a mixed model on the outcome at 4 months with a therapist random effect.

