## **9.3 Definition of Populations**

Analyses of all outcomes will be done according to the intent-to-treat principle, that is, subjects will be analyzed in the treatment group to which they were randomized. To include all subjects in the primary analysis (including those who have only baseline assessments), our primary analysis will be a mixed model over all measurements (including baseline) with the restriction that the two groups have equal means at baseline (i.e. the primary analysis will be a constrained longitudinal data analysis). Missing data, which hinders the ability to perform a strict ITT analysis, is inevitable in this pragmatic trial. However, we will try to minimize the amount of missing data by following the National Research Council's recommendations on strategies for preventing missing data in clinical trials (e.g. try to collect outcome data on subjects who discontinue therapy). Also, we have incorporated into the analysis plan (section 9.6) several sensitivity analyses for assessing the impact of missing data on the results.

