### **9.5.2 Secondary and Tertiary Outcomes**

Secondary outcomes will include BPI interference scores at 6 and 12 month post-baseline, and other outcomes collected via IVR automated call system at 4, 6 and 12 months post-baseline: NRS pain intensity rating, PEG-3 pain scale, depressive symptom severity (PHQ-8), pain catastrophizing, Insomnia severity index, Pain Self-Efficacy scale, Patient Global Impression of Change (4 months only), treatment dose and treatment satisfaction (collected at 4 months only).. Tertiary outcomes include time to treatment, time to completion, treatment completion (y/n), treatment fidelity/quality, treatment completion (y/n), and patient engagement (a patient attending at least one session of CBT-CP or completing at least one treatment week of COPEs). Details on the instruments used to collect these outcomes and their psychometric properties are provided in section 6.2.2, “Baseline Assessments.”

To evaluate the intervention delivery costs of COPEs and conduct a budget impact analysis. We will examine the intervention costs associated with COPEs(IVR-CBT-CP) including the cost of therapist time and technology costs. We will also examine VA service use across both treatment conditions (primary care, mental health, specialty care, emergency and urgent care visits).

To conduct a process evaluation using the Consolidated Framework for Implementation Research (CFIR) and RE-AIM to guide the evaluation. We will conduct CFIR-guided interviews with coordinating site clinicians and study site clinicians and administrators to assess their experience with and views regarding the strength and weaknesses of COPEs (IVR-CBT-CP) and synchronous CBT-CP interventions. We will also examine domains included in the RE-Aim model for both interventions.

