Sensitivity Analyses. If there is heterogeneity in therapist-specific time trends, then our primary analysis may have an inflated Type 1 error rate. As a first sensitivity analysis, we will use the 4-month outcome as the dependent variable in a mixed model ANCOVA. The model will have fixed effects for treatment, site, gender, baseline BPI interference, and a therapist random effect. To deal with missing data, this analysis will be applied to multiple imputed datasets (see Missing Data Sensitivity Analyses section). We will check whether the conclusion from this analysis regarding the treatment effect is consistent with the conclusion from the primary analysis.

As a second sensitivity analysis, we will use a mixed model similar to the primary analysis model, except that time will be treated as continuous. We will check the linear time assumption by considering other polynomials (e.g. quadratic, cubic).

Secondary Analyses. We will use Holm's correction to adjust for multiple secondary analyses. We will also conduct a per protocol analysis as an adjunct to the ITT primary analysis defining a "dose" of treatment as having attended/answered calls for 3 treatment sessions.

IVR-collected data. Analysis of the continuous secondary outcomes collected by IVR (PEG-3, PHQ-8, Pain Catastrophizing Scale, Insomnia Severity Index, Pain Self-Efficacy Scale,) will be similar to the primary analysis. We will use a generalized mixed model for ordinal data to analyze the Patient Global Impression of Change outcome.

We will compare treatment dose (number of sessions, a count variable) and treatment satisfaction at 4 months (continuous) between groups by using a negative binomial generalized linear mixed model and linear mixed model, respectively. The models will include treatment, site and gender as fixed effects, and a random effect for therapist.

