Missing Data Sensitivity Analyses: The inferences from the mixed model described above for the primary analysis are valid under the missing-at-random (MAR) assumption. This assumption cannot be verified based on the observed data, but we will perform sensitivity analyses to assess how results change under different missing data assumptions.

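### Month-4 treatment satisfaction is compared only among patients who answer at month 4, although the plan already builds imputed data sets that could bring in the rest; the visits and terms of the PGIC model also need stating

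*Combined protocol and SAP*

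**What the plan says.** Section 9.5.2 lists among the secondary outcomes "Patient Global Impression of Change (4 months only), treatment dose and treatment satisfaction (collected at 4 months only". Sections 6.1 and 6.2.4 agree that satisfaction is collected at month 4 alone.

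For the analysis, section 9.6 (Secondary Analyses) states: "We will compare treatment dose (number of sessions, a count variable) and treatment satisfaction at 4 months (continuous) between groups". Dose gets a negative binomial mixed model and satisfaction a linear one. On the terms: "The models will include treatment, site and gender as fixed effects, and a random effect for therapist". The Primary Analysis paragraph of the same section rules out any covariate other than site and gender in primary and secondary analyses.

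PGIC gets an ordinal generalised mixed model, with no visits, fixed effects or random effects named. The Précis (Design and Outcomes) and section 9.5.2 restrict it to month 4. The schedule in section 6.1 marks it at four follow-up visits: months 1, 4, 6 and 12.

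The missing-data part of section 9.6 opens with the primary outcome: "The inferences from the mixed model described above for the primary analysis are valid under the missing-at-random (MAR) assumption". Its multiple imputation generates 100 data sets from a model that includes primary and secondary outcomes at all time points. The plan names two analyses that will be run on these data sets in addition to the refit of the primary-type mixed models: the month-4 BPI ANCOVA and the exploratory propensity-score analysis.

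**The concern.** The repeated scales (PEG-3, PHQ-8 and the others) are analysed like the primary outcome. A patient who is lost after baseline or month 1 still contributes to those models, and the earlier values help to predict the missing month-4 value.

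Satisfaction has no such support. It has one value per patient, and a therapist random effect recovers nothing for a patient whose value is missing. The stated analysis is therefore a complete-case comparison. It makes no use of the BPI scores and session counts that will often be observed for the same patients.

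Section 5.4 reports that in the team's prior trials the most frequent drop-out point was after randomisation and before any session. Section 9.4 predicts a dose and time-to-treatment advantage for COPES and monitors whether engagement diverges between arms. If patients who never start are less satisfied, answer less often, and are more common in one arm, the responders in that arm are the more selected group and the arm looks better than it is. Satisfaction is a named secondary outcome, tested for superiority under Holm's correction.

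**Working it through.** **1. The plan's own figures (section 9.2).** Inputs: "Assuming a standard deviation of BPI interference of 2.4"; "80% power to detect a mean difference in BPI interference of 0.55"; "groups at 4 months using a two-sided t-test at significance level" 0.05; 305 per group evaluable; 20% attrition; 382 per group enrolled.

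- Normal-approximation sample size: n = 2 × (1.960 + 0.842)² × (2.4/0.55)² = 299 per arm, against 305 stated. Power at 305 per arm is 80.8%.
- Inflation: 305/(1 − 0.20) = 381.25, rounded up to 382 per arm, 764 in total. The figures reproduce.
- Standardised effect: 0.55/2.4 = 0.229 SD.

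**2. What the single-visit model loses.** At 20% attrition, 764 × 0.20 = 152.8 patients have no month-4 value and 611.2 remain. That matches the 610 planned, so the issue is bias and not a shortfall of power against plan. For reference, the detectable difference at 80% power is 0.227 SD with 305 per arm and 0.203 SD with 382.

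**3. Illustration of bias.** The documents give no attrition by arm, no non-response by starter status and no SD for satisfaction. Everything in this step is assumed.

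Let p be the proportion who never start, ms = 10% the non-response among starters, mn = 60% the non-response among non-starters, and g the starter-minus-non-starter gap in satisfaction (0.5 to 1.0 SD).

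Excess starter share among responders = (1−p)(1−ms) / [(1−p)(1−ms) + p(1−mn)] − (1−p).

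Bias = (excess in synchronous − excess in COPES) × g.

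Main scenario, p = 10% COPES and 30% synchronous:

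- COPES: 0.81/(0.81 + 0.04) = 95.3%, an excess of 5.3 points; 15% missing.
- Synchronous: 0.63/(0.63 + 0.12) = 84.0%, an excess of 14.0 points; 25% missing.
- Average missing: 20%, as planned. Difference: 8.7 points. Bias: 0.044 to 0.087 SD in favour of synchronous CBT-CP.

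| Never start, COPES / synchronous | Missing | Excess (points) | Difference | Bias, g = 0.5 to 1.0 | Relative to 0.229 SD |
|---|---|---|---|---|---|
| 10% / 30% | 15% / 25% | 5.3 / 14.0 | 8.7 | 0.044 to 0.087 SD | 19 to 38% |
| 10% / 20% | 15% / 20% | 5.3 / 10.0 | 4.7 | 0.024 to 0.047 SD | 10 to 21% |
| 5% / 30% | 12.5% / 25% | 2.7 / 14.0 | 11.3 | 0.056 to 0.113 SD | 25 to 49% |
| equal in both arms | equal | equal | 0 | 0 | 0 |

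**4. A simpler cross-check.** If non-responders would score s SD worse in both arms, bias = (difference in missing proportion) × s. With s from 0.25 to 0.5 this gives 0 at 20%/20%, 0.025 to 0.05 SD at 15%/25%, and 0.05 to 0.10 SD at 10%/30%. Equal attrition protects only if s is also equal: at 20% in both arms, a difference of 0.25 SD between the arms' values of s gives 0.20 × 0.25 = 0.05 SD.

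**5. The plan's two single-visit month-4 outcome models, side by side.** The BPI ANCOVA contains treatment, site, gender, baseline BPI and therapist, and is to be run on the imputed data. The satisfaction model contains treatment, site, gender and therapist, and has no statement on missing values. The one with less information in the model is the one left without imputation.

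**The case against.** **Follow-up may be better than feared.** Missed IVR assessments are pursued by telephone or mail (section 6.2.4), and patients withdrawn from treatment stay in follow-up (section 8). Stopping therapy is not the same as not answering the survey, and section 9.6 tabulates the two separately. This stands: the 60% against 10% contrast above has no support in the documents, and 20% is a planning figure for overall attrition.

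**The imputation already covers secondary outcomes.** True of the imputation model, so it would be too strong to say that missing data are handled for the primary outcome alone. But the completed data sets are to be analysed with models like the primary one, and satisfaction is not named. The other MAR sensitivity analysis adds baseline variables if they predict missingness. Even if it is read as reaching satisfaction, it uses no post-baseline information.

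**Stronger readings that the documents do not support.**

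- A reader might infer a breach of intention to treat from "Analyses of all outcomes will be done according to the intent-to-treat principle". Section 9.3 defines this as analysis by assigned arm, promises to include every subject only for the primary analysis, and concedes that missing data stand in the way of strict ITT. There is no contradiction.
- A reader might infer that PGIC is also complete-case. Section 9.6 names no visits or terms for its model, and the schedule has month-1 data, so this is undetermined. The lack of a baseline is inherent in a rating of change. Section 6.2.2 words it as improvement since treatment began, which has no clear meaning for a non-starter, so the illustration above should not be carried over to it.
- A reader might infer that the plan expects non-improvers to drop out. Section 9.6 gives this only as an example of a pattern that would point away from MCAR.

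**Dose.** The sentence on satisfaction also covers treatment dose. Dose comes from health records and the IVR system, so survey non-response does not affect it.

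**Conclusion.** The point holds for treatment satisfaction. As specified, its analysis uses only patients with a month-4 value, about 80% of those randomised if the planned attrition applies. It is unbiased only if missingness is unrelated to satisfaction given arm, site and gender. The plan already has a better tool and uses it for a comparable analysis.

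The size is not known. Under the assumptions shown, the bias lies between 0 and about 0.1 SD. The 0.229 SD yardstick belongs to BPI interference, since the plan gives none for satisfaction. In the main scenario the bias favours synchronous CBT-CP and so works against the trial's own superiority hypothesis; if non-start and non-response were higher in COPES, the direction would reverse.

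For PGIC the finding is narrower: the outcome list and the visit schedule differ on timing, and the model is not specified closely enough to tell which visits enter. Neither matter touches the primary analysis.

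**What to change.** **Satisfaction.** State in section 9.6 that month-4 satisfaction is analysed in the 100 imputed data sets with the model already given, combined by Rubin's rules. Name as imputation predictors BPI interference at all visits, sessions received and month-1 PGIC. The first two already belong to the imputation model as primary and secondary outcomes; month-1 PGIC should be listed explicitly because PGIC is a secondary outcome at month 4 only. Report the complete-case result alongside, with the number missing by arm.

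**PGIC.** Fit the ordinal mixed model to all collected visits, take the month-4 contrast as the secondary result, and write out the fixed and random effects. Reconcile the month-4 restriction in the Précis and section 9.5.2 with the four visits in section 6.1, for example by stating that month 4 is the tested endpoint and the other visits support the model.

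**Cost.** SAP wording and reuse of data sets already planned; no new data collection. The small downside is that the satisfaction result then relies on the imputation model, which is why the complete-case result should stay in the report.

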## **Interventions and Duration**

### COPES (IVR-CBT-CP)

Overview. COPES (IVR-CBT-CP) is a 10-week, IVR-facilitated program of CBT for chronic pain. The primary components of the intervention include: 1) a self-help handbook containing the rationale and instructions for using eight pain self-management skills, and their corresponding weekly skill practice goals; 2) a pedometer-facilitated walking program; 3) daily, automated IVR calls to collect patient-reported pain intensity and pain interference, sleep quality, pedometer-measured step count, and adherence to the pain coping skill practice ratings; and 4) weekly, two to four minute pre-recorded, personalized therapist messages based on participant IVR-reported data. The COPES IVR system provides participants the ability to automatically connect to the Veteran Crisis Line during any call. In this study, COPES will be centrally delivered from the VA Connecticut site. Participants will be given up to 14 weeks to complete treatment to allow for missed sessions (vacations, illness).

Intake and materials. Each weekly IVR module will feature a single self-management skill (e.g., paced physical activity, stretching, or relaxation) reinforced via a companion chapter in the patient handbook. The handbook, developed for the initial COPEs efficacy trial and refined prior to the ongoing COPEs implementation trial, is written at the 6th grade reading level and features design strategies to enhance engagement and readability. The manual will assign a specific goal each week that promotes practice of the module's coping skill (e.g., practice deep breathing for 5 minutes each day this week). The participant will be instructed to practice that week's skill each day of the week and report via daily IVR assessment their daily skill practice completion (0=not at all completed to 10=totally completed). Participants will have access to a patient handbook through the COPEs website. If patients do not have Internet access the handbook will be mailed to them. Participants will also be mailed an Omron Go Smart Model HJ-112 pocket pedometer to facilitate their participation in the walking portion of the treatment.

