per week. Patients set goals with their therapists and are asked to regularly practice the pain coping skills they are learning in treatment at home. Therapists give feedback regarding goal accomplishment. Although all CBT-CP therapists have undergone training and demonstrated CBT-CP specific competencies, it is anticipated that they will still display a range of experience and skill in delivering the intervention and maintaining fidelity to the treatment manual. In the spirit of pragmatic trials, we will not attempt to impose fidelity to the treatment manual, or provide specific training or feedback, but we will monitor basic measures of treatment fidelity based on items from the checklist that will be developed. Using electronic health record clinical notes we will track participant dose (number of weeks engaged), time to first treatment session, time to completion, and treatment completion (yes/no). Thus, synchronous-CBT-CP will be delivered as it would in usual clinical practice.

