## 5.4 Engagement, Adherence, and Completion Assessment

We will track time to treatment, dose, engagement (did the participants begin treatment) as well as adherence (how many sessions did the participant attend), time to complete treatment, and completion (attend all 10 treatment sessions/weeks yes/no).

**Engagement.** Because the most frequent drop out point in our prior trials has been after randomization, but prior to attending any treatment sessions, we will track participant engagement (did the participant begin treatment). Patient engagement will be defined as a patient attending at least one session of CBT-CP or completing at least one treatment week of COPEs.

**Dose.** We will track participant adherence (number of weeks engaged in IVR-CBT and number of sessions attended in in-person CBT-CP).

**Completion.** We will identify the number of participants who complete all 10 treatment sessions (completion=yes/no).

Engagement, adherence, and completion will be identified for COPEs (IVR CBT-CP) patients by measuring number of weeks that the participant was participating in COPEs (at least one call answered/week through the COPEs IVR system and in synchronous CBT-CP through examining number of treatment sessions attended as

documented by treatment notes in the electronic health record. For workload credit and co-payment billing purposes all synchronous sessions are recorded in the VA electronic health record. Study staff will collect session attendance and treatment format data at the same time that they do the post-treatment chart review for adverse events. We will perform subgroup analyses for the primary outcome and engagement.

Variable	Collection
Time to treatment from randomization (access- time to first treatment session)	Collected from electronic health record review by study RAs.
Number of treatment sessions received (burden- dose)	Number of sessions (weeks for IVR) attended
Engagement-Did participant complete one session	Collected from electronic health record review by study RAs using notes or CPT codes
Time taken to finish treatment	Number of days between randomization and last treatment session
Fidelity / quality assurance	Treatment quality checklist for both conditions. Assess presence of pain coping skill teaching, treatment session length (synchronous) skill practice, homework assignment and assessment of adherence to practice.
Treatment characteristics	Format (in-person, VVC, Skype) and mode (individual/group)

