## 9.4 Interim Analyses and Stopping Rules

We acknowledge that of the rationale for superiority of IVR CBT has diminished because instead of in-person treatment, control participants can now obtain videoconference or telephone CBT-CP from their homes. However, we still expect IVR CBT will be superior. We assume that dose will be greater in the IVR condition because patients can access treatment at any time, not just during business hours and session time is shorter reducing therapist and participant burden relative to the control condition. Time to treatment will be shorter in IVR because the centralized delivery of IVR CBT allows more efficient use of therapist resources. There is relatively little information reported in the literature about dose in videoconference treatment and none about time to treatment relative to in-person treatment so there is little information to guide these estimates more precisely. We have proposed to monitor these and other factors that we believe will continue to be different, and show an advantage for the IVR condition, as part of the trial (see below).

**Monitoring Separation Between Arms:** We will monitor indicator variables (below) on treatment delivery, uptake and quality to determine whether the treatment arms are diverging in ways expected to drive differences in clinical outcomes. We will continuously monitor the indicators and calculate the means and confidence intervals of each indicator for both groups and for the difference between groups. These data will be shared with the DSMB at the regularly scheduled DSMB meetings occurring every 4 months and at 50% of participant treatment completion and used to assess whether there is divergence between the treatment conditions. These data may be used to inform a future futility analyses if needed once adequate data is collected [50% participants (n=382) completed treatment].

Indicator	Description
Dose	# of sessions/weeks attended including only those with $\geq 1$ session
Engagement	% who initiate treatment (attend first treatment session)
Minimal dose	% who achieve minimal dose (minimal dose=3 sessions/weeks)
Time to treatment initiation	Time from randomization to first treatment session or IVR call among those with $\geq 1$ session
Quality assurance	Ratio of #skills taught/#sessions among those with $\geq 1$ session

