Tertiary Analysis Engagement/Dose/Completion. Patient engagement will be defined as a patient attending at least one session of CBT-CP or completing at least one treatment week of COPEs. Time from randomization to treatment, time from randomization to completion, completion (y/n, a binary variable) will be examined. For workload credit and co-payment billing purposes all sessions are recorded in the VA electronic health record. Study staff will collect session attendance data at the same time as they do the post-treatment chart review for adverse events. We will compare engagement, and completion between groups by using logistic generalized linear mixed models. Time to treatment and time to completion will be analyzed using Cox proportional hazards models. All models will include treatment, site and gender as fixed effects, and a random effect for therapist.

Recruitment Method: Patients will be recruited by 2 different approaches (provider referred or self-referred). We plan to examine potential differences in patient characteristics by recruitment type. First, we will present descriptive statistics for recruitment type in each treatment arm and overall in Table 1. If the sample sizes in the two recruitment type groups are sufficient ( $\geq 30$  in each group), we will include a supplemental table comparing the two groups on the baseline characteristics included in Table 1. We will compare baseline continuous characteristics using a t-test or Wilcoxon rank sum test, and categorical characteristics using the chi-square test or Fisher's exact test as appropriate.

Subgroup Analyses. To test whether between-group differences in outcome vary by gender, race/ethnicity comorbid substance use disorder, and alcohol use subgroup analyses will be performed via interaction tests. For example, to perform the race subgroup analysis for the primary outcome, we will enter race, the interactions race-by-time, race-by-treatment and race-by-time-by-treatment into the primary analysis models: the last two interactions will allow us to test whether race is a moderator of the treatment effect. We will perform subgroup analyses for the primary outcome and engagement. Subgroup analyses for other outcomes and subgroups (such as PTSD, depressive disorder) may be conducted as exploratory analyses.

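### A single Cox hazard ratio for time to completion depends on a censoring date the plan does not give, because COPES completions fall in a bounded window and no limit is stated for synchronous CBT-CP

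*Combined protocol and SAP*

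**What the plan says.** **Analysis.** Section 9.6 (tertiary analysis of engagement, dose and completion) sets out the time outcomes: "Time from randomization to treatment, time from randomization to completion, completion (y/n, a binary variable) will be examined". It then says: "Time to treatment and time to completion will be analyzed using Cox proportional hazards models". On model terms: "All models will include treatment, site and gender as fixed effects, and a random effect for therapist". It gives no proportional-hazards check, no censoring date and no rule for participants who never complete.

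**COPES timing.** The Précis and Section 5.1 agree: "COPES (IVR-CBT-CP) is a 10-week, IVR-facilitated program of CBT for chronic pain", and "Participants will be given up to 14 weeks to complete treatment to allow for missed sessions (vacations, illness". Both place seven days of baseline calls before treatment.

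**Synchronous timing.** The Précis says: "Thus, synchronous-CBT-CP will be delivered as it would in usual clinical practice". Section 5.2 leaves local adaptations alone. None of these passages states a time limit for completing.

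**Passages that leave room for doubt.** Section 8 mentions a 14-week cutoff counted from baseline, for people who re-enrol after withdrawing, and names no arm. The Section 5.4 table records time to finish as "Number of days between randomization and last treatment session", which also exists for someone who stops early. Section 9.6 collects attendance at the post-treatment chart review. Section 6.2.2 reviews synchronous records when treatment ends. Section 7.3 has charts examined at each follow-up assessment, and the last of these is at 12 months.

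**The concern.** A Cox model with one treatment term assumes that the ratio of the two completion rates stays constant over follow-up. Here the COPES rate is zero before its window opens and zero after it closes, while the synchronous rate can stay above zero for months. The fitted ratio is then an average of an early COPES lead and a later synchronous catch-up, weighted by where events fall before the cut.

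Sections 1.2 and 9.1 state superiority hypotheses for the tertiary outcomes, so this ratio will be read as evidence. How many participants complete already has its own logistic model in Section 9.6, so the time analysis should show how fast they complete. A hazard ratio mixes the two, and with no stated censoring date the mix can be settled after the data are seen.

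**Working it through.** **Plan's own figures.** No hazard ratio, event count or power is stated for either time outcome. The sample of 382 per group comes from the primary outcome: 305 / (1 − 0.20) = 381.25, rounded up. I use 382 per arm.

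**COPES window, in weeks from randomisation.** I assume calls start promptly.
- Earliest: 1 (run-in) + 9 = 10 if completion counts on entering the tenth treatment week, or 1 + 10 = 11 at its end.
- Latest: 1 + 14 = 15 if the allowance runs from treatment start, or 14 if it runs from baseline.

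**Consequence.** Let h_C(t) and h_S(t) be the completion hazards for COPES and synchronous CBT-CP. After about week 15, h_C = 0. If h_S > 0 there, the ratio h_C/h_S is 0, so it cannot be constant unless it is zero throughout. This step needs no assumed rates, only some synchronous completions after week 15.

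**Weekly hazards in one assumed case.** Completion 40% COPES and 50% synchronous; synchronous time = 10 weeks + exponential wait (mean 4) + exponential slippage (mean 6).

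| Weeks | COPES | Synchronous | Ratio |
|---|---|---|---|
| 11–12 | 0.1953 | 0.0222 | 8.8 |
| 12–13 | 0.1649 | 0.0323 | 5.1 |
| 13–14 | 0.1151 | 0.0374 | 3.1 |
| 14–15 | 0.0396 | 0.0415 | 0.95 |
| 15–20 | 0 | 0.0425 | 0 |

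**Cox hazard ratio (COPES vs synchronous) by common cut-off, non-completers kept at risk.** Simulated with treatment as the only term. All rates and waits are assumptions.

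| Completion COPES/synchronous | Mean wait, slippage (weeks) | 15 wk | 4 mo | 26 wk | 52 wk |
|---|---|---|---|---|---|
| 40/50 | 8, 6 | 4.50 | 2.92 | 1.40 | 0.96 |
| 40/50 | 4, 6 | 3.66 | 2.25 | 1.18 | 0.95 |
| 45/55 | 4, 6 | 3.86 | 2.39 | 1.25 | 1.00 |
| 50/50 | 4, 6 | 4.96 | 3.08 | 1.64 | 1.33 |
| 60/40 | 4, 6 | 8.27 | 5.19 | 2.85 | 2.36 |
| 20/70 | 1, 2 | 0.21 | 0.19 | 0.18 | 0.18 |

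The first row uses 9 rather than 10 fixed weeks for synchronous treatment and a cut at 17 weeks for 4 months. Its synchronous completers finish on average at 8 + 9 + 6 = 23 weeks, against 15 at the latest for COPES. In the 45/55 row the medians among completers are 12.2 and 18.3 weeks, yet only 7% of trials reject at 52 weeks.

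**Non-completer rule.** In the 45/55 row, censoring COPES non-completers at week 15 while following synchronous patients to 52 weeks gives 3.86 instead of 1.00.

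**Alternative summary.** Restricted mean time to horizon τ is the mean of min(T, τ), with T infinite for non-completers. In the 45/55 row the difference (COPES minus synchronous) is −1.5 weeks at 4 months and −2.2 weeks at 26 weeks, rejecting in all runs. At 52 weeks it is −0.2 weeks, rejecting in 5%.

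**Power at matched horizons** (ranges reflect different assumed spreads of completion times):
- 26 weeks, 40/40: Cox 63–74%, restricted mean 99–100%.
- 26 weeks, 40/45: Cox 25–32%, restricted mean 86–97%.
- 52 weeks: 35% vs 42% (40/40) and 9% vs 10% (40/45).

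**Time to treatment.** The 14-week allowance does not enter. With assumed starts of 85% COPES vs 70% synchronous, the ratio moves from 2.92 (8-week cut) to 2.22 (52-week cut). At 75/75 it moves from 1.95 to 1.42. Both reject in at least 98% of runs. At 75/85 it moves from 1.64 to 1.15, and rejection falls from 100% to 45%.

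**The case against.** The defence has real force on several points.

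- **The plan does not keep non-completers at risk to 52 weeks.** True: it is silent. With an early cut, or with COPES non-completers censored at week 15, the ratio is large and nothing is hidden. That moves the gap to an unstated rule on which the answer turns; it does not close it.
- **The absence of a synchronous limit is inferred from silence.** True, and the Section 8 cutoff could be read as covering either arm. If it bound both arms, the late synchronous tail would shrink or vanish.
- **The null results need synchronous completion similar to or above COPES.** True. Sections 9.1 and 9.4 expect a greater COPES dose. When COPES completes more often (50/40, 60/50), power is about 100% for all methods, though the ratio still moves with the cut (1.79 to 1.68 and 1.89 to 1.77 between 26 and 52 weeks).
- **Restricted mean time also depends on its horizon.** True, as the 52-week result shows. Setting Cox at 52 weeks against restricted mean time at 26 weeks would credit the method with what is largely an effect of the horizon. At a matched 26 weeks a real advantage remains.
- **Completion yes/no is already analysed, and the outcome is tertiary.** Both true, and both limit the weight of the point.

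**Conclusion.** The point holds for time to completion. Proportional hazards fails if any synchronous patient completes after about week 15, and the single ratio then has no fixed meaning without a censoring date and a non-completer rule. Under assumed 40% vs 50% completion it runs from about 4.5 to about 1.0 across cut-offs from 15 to 52 weeks. These sizes rest on assumed completion rates and waits, on prompt COPES starts, and on no synchronous limit applying.

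Four stronger readings are not supported:
- **That the hazards must cross.** Crossing needs COPES to lead early. Section 9.4 points that way for starting treatment ("Time to treatment will be shorter in IVR because the centralized delivery of IVR CBT allows more efficient use of therapist resources"), but in the 20/70 case synchronous CBT-CP leads throughout and there is no crossing.
- **That Cox always hides the difference, or reverses it.** It is hidden only with similar or higher synchronous completion and a late cut. The lowest ratio in the 40/50 and 45/55 cases was 0.95, with 9% of runs rejecting, so no reversal is shown.
- **That time to treatment fails in the same way.** The 14-week allowance governs finishing, not starting. Any non-proportionality there comes from the run-in and local waits, and in the cases tested it is milder.
- **That the primary result is at risk.** It is unaffected.

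**What to change.** For time to completion only, amend Section 9.6:

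1. Define the event as completing all 10 sessions or weeks, and separate it from the last-session date in the Section 5.4 table.
2. Name one censoring date counted from randomisation, the same in both arms, and keep non-completers at risk until then.
3. Make the restricted mean time difference to a fixed 6-month horizon from randomisation the main estimate and test. Report cumulative completion at 4, 6 and 12 months, with curves.
4. Adjust for site and gender, and allow for therapist clustering, for example by cluster-robust or bootstrap standard errors. Section 9.2 assumes only 9 COPES therapists, so clustering should not be dropped.
5. Keep the Cox model as a supplement at the same censoring date.

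Reconcile the 14-week cutoff in Section 8 with the allowance in the Précis and Section 5.1, and state which arm it covers and from when it counts.

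For time to treatment, keep Cox, with a stated common censoring date and a proportional-hazards check.

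The cost is SAP wording and a standard routine, with no new data. The downsides are two numbers (how fast, how many) in place of one, and a restricted mean result that applies only to the chosen horizon.
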